9.1.3 B - Notification to Regulatory authorities, Investigators and IRBs

Detailed SAE processing, distribution and reporting is provided in the Safety Management Plan. Sponsor and/or CRO(s) inform Investigators, IRBs/IECs and regulatory authorities of any Suspected Unexpected Serious Adverse Event Reactions (SUSARs) occurring in the study or other Sponsor studies of the investigational product, as appropriate per local reporting requirements.

9.2 B – Clinical local laboratory assessments

Blood samples for determination of the hematology panel, the comprehensive metabolic panel and the coagulation panel are taken at the times indicated below and in the Schedule of Assessments. No fasting is required.

Sample collection times are as follows:

- During screening, approximately 45 minutes preceding initiation of study drug. Note, a blood draw for assessment of potassium must always be drawn after informed consent and prior to enrollment; however, if results are available for any or all other parameters from a blood draw prior to screening (up to 24 hours prior to IC), there is no need for a new blood draw for those parameters.
- At 90 minutes post dose

The following laboratory safety variables are measured and analyzed at the local laboratory:

INSTANT Study

Clinical Study Protocol

Study no. FLE-002

Version 8.0 EU-1 Page: 69 of 117

Hematology panel: performed at screening and may include some or all of the following parameters (use the site's standard hematology panel, also known as complete blood count with differential):

- Red blood cell (RBC) count
- Hemoglobin
- Hematocrit
- Mean corpuscular volume (MCV)
- Mean corpuscular hemoglobin (MCH)
- Mean corpuscular hemoglobin concentration (MCHC)
- Red cell distribution width (RDW)
- White blood cell (WBC) count
- Neutrophils
- Lymphocytes
- Monocytes
- Eosinophils
- Basophils
- Platelet count
- Mean platelet volume (MPV)

Comprehensive metabolic panel (CMP): performed at screening and at 90 minutes post dose and may include some or all of the following parameters (use the site's standard comprehensive metabolic panel):

- Glucose and calcium
- Kidney function tests (serum creatinine*, to derive the estimated creatinine clearance [mL/min/1.73m²], and blood urea nitrogen [BUN])
- Proteins (total protein and albumin)
- Electrolytes (potassium*, sodium, chloride, bicarbonate)
- Liver function tests (total bilirubin [TBL], conjugated bilirubin [e.g., if TBL is elevated], aspartate aminotransferase [AST], alanine aminotransferase [ALT], and alkaline phosphatase [ALP])
- * = parameter is required for evaluation of eligibility and must be collected at screening

Coagulation panel: performed at screening and includes at least of the following parameters (use the site's standard coagulation panel):

- Partial thromboplastin time (PTT)
- Prothrombin time (PT)
- Thrombin time (TT)
- Fibrinogen

Pregnancy: female subjects of childbearing potential that undergo screening after IC signature need to have either a serum or urine pregnancy test.

INSTANT Study Clinical Study Protocol

Study no. FLE-002

Version 8.0 EU-1 Page: 70 of 117

Laboratory reports are filed with the source documents. The Investigator must review the laboratory reports, document this review, and record any clinically significant abnormal laboratory results occurring during the study as adverse events. Clinically significant abnormal laboratory findings are those which are not associated with the underlying disease, unless judged by the Investigator to be more severe than expected for the subject's condition. If laboratory values from non-protocol specified laboratory assessments performed at the institution's local laboratory require a change in subject's management or are considered clinically significant by the Investigator, then the results must be recorded in the eCRF.

9.2.1 B - Total blood volume

Blood samples for PK analysis (Section 8.1 B) and for laboratory safety assessments (Section 9.2 B) are collected for each subject periodically on Day 1, resulting in the following total blood volume, in mL, per subject per assessment type:

-	Pharmacokinetic assessments (a maximum of 9 samples of 4.0 mL))	36.0 mL
-	Clinical local laboratory assessment (screening)		12.5 mL
-	Clinical local laboratory assessment (discharge)		7.0 mL
		Total	55.5 mL

The total blood volume of 55.5 mL corresponds to approximately 3.75 tablespoons.

9.3 B - Vital signs

Heart rate, systolic and diastolic BP, respiratory rate (breaths/min), oxygen saturation (SpO_2), and body temperature are recorded from the cardiac telemetry monitoring according to the Schedule of Assessments (Section 17.4). Body temperature is only recorded at screening.

When time points coincide for blood draws and vital signs assessment, blood draws will be performed prior to vital signs assessments.

9.4 B - Other electrocardiograms

Other original routine ECGs obtained at the site or printouts of the telemetry rhythm strip performed according to local clinical practice are stored in the subject's medical record as source documentation.

9.5 B - Physical examination

A physical examination is performed by medically qualified individuals. The targeted examination includes general appearance, cardiovascular, respiratory (including lung auscultation), abdomen (liver and spleen) and neurological evaluations. Results are recorded as normal or abnormal per evaluation with a listing of abnormalities in the eCRF. Height, weight and derived BMI are also measured and recorded in the eCRF at screening.

INSTANT Study Clinical Study Protocol

Study no. FLE-002

Version 8.0 EU-1 Page: 71 of 117

9.6 B - Handheld echocardiogram (HHE)

To evaluate the subject's eligibility during screening (e.g., LVEF, valvular disease, structural heart disease), a diagnostic echocardiogram with a Sponsor-provided handheld portable ultrasound device will be required at screening for US subjects if the subject does not have results from a standard diagnostic echocardiogram (including LVEF) within the 6 months prior to screening. For information on the HHE Sub-Study available to EU subjects, refer to Section 17.5.

The following data will be recorded from the HHE in the eCRF:

- Date and time HHE is administered
- Who performed the HHE (e.g., professional title or study role)
- Date and time HHE report/results became available
- Who analyzed the echocardiogram obtained (e.g., professional title or study role)
- The following assessments will be recorded:
 - LV size
 - o LVEF
 - LV hypertrophy
 - Valvular disease
 - Other clinically significant findings

The HHE data will be submitted to an independent reviewer to compare with the HHE assessments made by the site staff during the screening period; however, this independent review will not be used for the assessment of Part B subject eligibility during screening. This independent review will only be used to explore if site staff made a successful assessment of subject eligibility using the HHE data obtained during screening.

10 B - Statistical methods

Statistical analyses for Part B will apply to all Part B subjects, including those EU subjects participating in the Handheld Echo Sub-Study (refer to Appendix 6). Data from the HHE Sub-Study are collected on a subset of the Safety Population for Part B and the Part C Medically-Led Cardioversion Study. The analysis for the additional echocardiogram data measured will be separate from the safety analyses of all Part B subjects and Part C subjects in the Medically-Led Cardioversion Study.

10.1 B - Study populations

10.1.1 B - Population of consented subjects

The population of consented subjects includes all subjects who signed the informed consent form.

INSTANT Study Clinical Study Protocol

Study no. FLE-002

Version 8.0 EU-1 Page: 72 of 117

10.1.2 B - Intention-to-treat population (ITT)

The intention-to-treat (ITT) population includes all subjects that were enrolled. Compared to the population of consented subjects, the ITT population excludes subjects who are not enrolled. The population does include subjects who were enrolled when re-entering the study for a new episode of AF.

10.1.3 B - Modified ITT population (mITT)

The modified ITT population includes all enrolled subjects who received the full assigned dose of study drug and were in AF at the time of start of the inhalation of the study drug. Subjects whose AF converted to SR prior to completion of the assigned full dose of study drug will also be included in the mITT population.

10.1.4 B - PK population

The PK population includes all enrolled subjects who received the full assigned dose of study drug irrespective of whether the subject was in AF or not at the initiation of dosing. Compared to the Safety population the PK population excludes subjects who did not receive the full assigned dose of study drug.

10.1.5 B - Safety population

The Safety population includes all enrolled subjects who started the inhalation of study drug, whether the subject was in AF or not and whether the subject received the full assigned dose of study drug or not. Compared to the ITT population, the Safety population excludes subjects who are enrolled but did not start of the inhalation of study drug.

10.2 B – Statistical analyses

The primary endpoint analyses of Part B will be based on Part B subjects alone. If the Part B primary endpoint analysis meets the pre-specified criteria for significance and is not substantially different from Part A 120 mg FlecIH-103, the two dose cohorts (120mg FlecIH-103 cohorts from Part A and Part B) will be combined for the overall analysis of Part B to provide a more precise estimate of efficacy, safety, and PK/PD.

This protocol provides general aspects of the statistical methods. Specific details are outlined in the Statistical Analysis Plan (SAP).

10.2.1 B - Efficacy analyses

Modified ITT population

The mITT population will be used to evaluate all primary and secondary efficacy endpoints.

Statistical analyses of secondary efficacy endpoints

Hierarchical testing and adjustments for multiplicity will not be applied in the evaluation of efficacy.

INSTANT Study Clinical Study Protocol

Study no. FLE-002

Version 8.0 EU-1 Page: 73 of 117

10.2.1.1 B - Statistical analysis of the primary efficacy endpoint

The endpoint of conversion to SR is defined as the presence of SR, derived from the AECG, lasting for at least 1 minute. The first conversion to SR that lasts for at least 1 minute is referred to as the index conversion. Any conversion not lasting for at least 1 minute is not considered an index conversion.

The conversion rate (%) of recent onset of AF to SR, within 3 hours, ranges from 2-14% spontaneously²² and with placebo^{51, 52} approximately $16\%^3$. In more recent studies such as those with vernakalant, the reported placebo conversion rate was ~5 $\%^4$. For this study, we have selected a somewhat higher placebo conversion rate of 20%. In order to statistically evaluate whether the proportion of subjects whose AF converted to SR by inhaled flecainide within 90 minutes after initiation of dosing is > 20%, the following hypotheses are evaluated at a one-sided significance level of 0.05:

 $H_0: \rho = 20\%$

The one-sided alternative hypothesis is:

 $H_A: \rho > 20\%$

The null hypothesis is tested with the use of an exact binomial test. A 90% Clopper-Pearson confidence interval is computed for the proportion of subjects who met the primary endpoint. If the lower bound of the 90% confidence interval is > 20% then the null hypothesis is rejected in favor of the alternative, i.e. there is sufficient evidence to conclude the percentage of subjects AF converting to SR is > 20%.

10.2.1.2 B - Statistical analysis of proportion of subjects who convert within 90 minutes after initiation of dosing and have C_{max} values ≥ 200ng/mL (e.g., 200, 300, 400, and 500 ng/mL)

This endpoint is defined as the number of subjects who meet the endpoint criteria, divided by the total number of subjects included in the analysis. The estimate for the conversion rate and its associated 95% Clopper-Pearson Cls will be derived.

For the purpose of this study, C_{max} is defined as the peak plasma level of flecainide prior to administration of any alternative pharmacological agent (e.g., oral flecainide).

INSTANT Study Clinical Study Protocol

Study no. FLE-002

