4.2 B - Exclusion criteria

Subjects are NOT eligible to participate in this study if they meet ANY of the following exclusion criteria:

General

- 1) Subject < 18 or > 85 years of age
- 2) Hemodynamic and/or cardiac instability, with systolic blood pressure < 100 mmHg or > 150 mmHg, or ventricular heart rate < 80 bpm or > 160 bpm. For subjects to meet eligibility criteria for Part B or the Part C Medically-Led Cardioversion Study, at least 2 of the 3 measurements of vital signs during screening (45, 30, and/or 15 minutes prior to dosing) must meet the stated criteria. For subjects to meet eligibility criteria for the Part C Patient-Led Under Medical Supervision Cardioversion Study, the measurement of vital signs taken within 10 minutes prior to dosing must meet the stated criteria.

INSTANT Study Clinical Study Protocol

Study no. FLE-002

Version 8.0 EU-1 Page: 44 of 117

3) Current AF episode has been treated with Class I or Class III antiarrhythmic drugs or electrical cardioversion. Subjects whose current AF episode has been treated with flecainide are eligible if their total cumulative exposure to flecainide (including the study drug to be administered in this study) does not exceed 320 mg within a 24-hour period, per site standard of care.

Relevant structural heart disease

- 4) History of acute decompensated heart failure (HF)
- 5) Evidence of significant HF defined as any of the following:
 - a) Hospitalization in the last 12 months for HF or suspected HF event
 - b) Most recent assessment of left ventricular ejection fraction (LVEF) < 45%
 - i) For patients in the US, a standard diagnostic echocardiogram assessed ≤ 180 days prior to screening is required to ascertain eligibility. If none is available, the patient must undergo a standard diagnostic echocardiogram or a diagnostic echocardiogram using a portable ultrasound device (handheld echocardiogram [HHE]) during screening to confirm eligibility.
 - ii) For patients in the EU who are participating in the optional HHE Sub-Study, the patient must undergo an HHE during screening to confirm eligibility.
 - c) New York Heart Association (NYHA) Class II-IV symptoms
 - d) Medication history suggestive of HF per the Investigator's discretion

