10.3 B - Sample size determination

In Part B, the estimated sample size of 25 mITT subjects for the 120 mg dose cohort is based upon the evaluation of the following statistical hypotheses using an exact binomial test, H_0 : $\rho = 20\%$ versus H_A : $\rho > 20\%$ ($\alpha = 0.05$).

Given the actual conversion rate for the Part A 120 mg dose cohort is 44%, a sample size of 25 subjects has 84% power to reject the null hypothesis (H_0) in favor of the alternative (H_A) with a one-sided significance level of 0.05. The null hypothesis is rejected when at least 9 subjects' AF converts to SR within 60 minutes after initiation of dosing.

If 9 subjects' AF converts to SR, the resulting conversion rate is 36% with a 90% exact binomial confidence interval of [20.24%, 54.39%]. If 9 or more subjects' AF converts to SR, the lower bound of the 90% exact binomial confidence interval will be greater than 20.24%. When the lower bound of the 90% confidence interval for conversion rate is greater than 20%, there is sufficient support for the rejection of the null hypothesis in favor of the alternative.

It is expected approximately 20 subjects will participate in the Handheld Echo Sub-Study in Part B and the Part C Medically-Led Cardioversion Study; however, the Sub-Study does not have a minimum or maximum enrollment target.

Study no. FLE-002

Version 8.0 EU-1 Page: 78 of 117

XII. Study protocol (Part C - EU only): Medically-Led Cardioversion and Patient-Led Under Medical Supervision Cardioversion Studies

2 C - Study objectives

All Part C objectives are exploratory:

- To explore the feasibility of patient-led self-administration of flecainide acetate inhalation solution in a hospital setting under medical supervision
- To explore the PK/PD of flecainide acetate inhalation solution in subjects with recent onset of paroxysmal AF for patient-led administration relative to medically-led administration, including resumption of SR
- To explore the feasibility of implementing a portable cardiac ultrasound (HHE) at screening in an emergent setting

3 C - Study design

Part C is conducted in Europe only. Part C comprises two distinct studies, a Medically-Led Cardioversion Study (procedures are identical to those in Part B) and a Patient-Led Under Medical Supervision Cardioversion Study (procedures include the subject self-preparing and self-administering the study drug under medical supervision in the clinic).

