### **8.7.4 Pooled MLS Predose Flecainide Cohort (Cohort 4)**

This Cohort includes all subjects in the study population (i.e., safety, mITT etc.) who are part of the Pooled MLS Cohort (Cohort 2) and have flecainide present in their predose PK sample (i.e., flecainide plasma concentrations > 0 ng/mL). This Cohort will be referred to as Cohort 4.

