## FLE-002 (INSTANT) – Final Analysis

## Statistical Analysis Plan

Analysis is performed for the mITT population. A Subject meets the endpoint if conversion occurred within 90 minutes after initiation of dosing without the use alternative medication (e.g., IV flecainide and propafenone) or procedures (e.g., ECV). If a subject's conversion status is unknown, then the analysis will assume that the subject did not convert.

The percentage is calculated as:

$$p = 100 * (\text{number of converted subjects} / \text{number of subjects in mITT population})$$

A 90% exact binomial confidence interval will be calculated for the percentage.

No formal testing will take place. Analysis will not be performed for the PLS population.

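### The Part B primary test sets a no-drug rate of 20% against a population that may already carry flecainide for the same episode, so some conversions may be wrongly credited to the inhaled dose; the effect on the 5% error is possible but of unknown size

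*Protocol*

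**What the plan says.** **Benchmark.** Protocol 10.2.1.1 B cites conversion within 3 hours of 2-14% spontaneously and about 16% on placebo, and about 5% on placebo in more recent trials. It then states: "For this study, we have selected a somewhat higher placebo conversion rate of 20" percent. The synopsis calls this a historical placebo rate. The test is an exact binomial test, where "the following hypotheses are evaluated at a one-sided significance level of 0.05".

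**Entry.** Exclusions 3 and 20 (Protocol 4.2 B) carry an exception: "Subjects whose current AF episode has been treated with flecainide are eligible if their total cumulative exposure to flecainide", study drug included, stays within 320 mg in 24 hours. No minimum interval before study dosing is given. Patients on a pill-in-the-pocket regimen of flecainide or propafenone are a named pre-screening group.

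**Analysis set.** Under Protocol 10.1.3 B, "The modified ITT population includes all enrolled subjects who received the full assigned dose of study drug and were in AF" when inhalation started. Subjects who convert before finishing the dose are also kept. Earlier flecainide is no bar. SAP 8.5 follows the same rule.

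**Success rule.** SAP 9.2.1 counts a conversion within 90 minutes of starting the dose "without the use alternative medication (e.g., IV flecainide and propafenone) or procedures (e.g., ECV"). SAP 3.2 attributes such a conversion to the study drug. Neither says how flecainide taken before T0 is treated.

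**Final SAP.** SAP 8.7.4 defines Cohort 4 as pooled subjects who "have flecainide present in their predose PK sample". Cohort 3 is the remainder and includes subjects whose predose sample is missing (SAP 8.7.3). Table 1 gives mITT efficacy for both, but the split exists only in the pool of Parts A, B and C. Cohort 1 (Part C, medically led) is not split, and SAP 9.2.1 plans no formal test.

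**The concern.** A single-arm test against a historical rate supports a drug effect only if the historical rate describes what the same patients would do without that drug. Here the rate comes from untreated and placebo patients, while some trial subjects may have an active antiarrhythmic on board from before T0. The protocol's own figures make carry-over plausible: inhaled flecainide has an elimination half-life of 9-12 hours (1.2.2), and an IV dose of about 150 mg stays above 200 ng/mL for about 120 minutes (1.5). If study drug is counted as 120 mg, the cap leaves 320 - 120 = 200 mg of possible earlier exposure.

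The attribution of conversion to inhaled flecainide is at stake. With zero effect of the inhaled dose, the expected success rate in a mixed population is a weighted average of the no-drug rate and the pre-dosed subjects' residual rate, and that average can exceed 20%.

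**Working it through.** **1. The plan's own figures.** Inputs: n = 25, reject at 9 or more, null 20% (synopsis; Protocol 10.3 B).

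- Size: P(X >= 9 | 25, 0.20) = 4.68%.
- Power: 92.0% at 48% (the synopsis says at least 92%) and 84.3% at 44% (10.3 B says 84%).
- 90% exact interval for 9/25: 20.24% to 54.39%, as stated.

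The arithmetic of the design reproduces. The two passages differ on the assumed rate (48% against 44%) and on the window in the rejection rule (90 against 60 minutes); that is a separate matter.

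**2. Model under zero effect of the inhaled dose.** Let m of the 25 be pre-dosed and convert within 90 minutes at rate q, and let the other 25 - m convert at the true no-drug rate b. Then

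P(false rejection) = P(X + Y >= 9), with X ~ Bin(m, q) and Y ~ Bin(25 - m, b),

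and the expected rate is [(25 - m)b + mq]/25.

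**3. Inputs that are assumed.** The documents give neither m nor q.

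- m: 3, 5 and 10 of 25, for illustration.
- q: 33% to 48%, borrowed from the Part A conversion rates in Protocol 1.4 (33% at 60 and 90 mg, 41% and 48% at 120 mg).
- b: 20% (the null itself), then 16%, 14% and 5% from the rates cited in 10.2.1.1 B.

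For m = 5 and b = 20% the expected rate is (4.0 + 1.65)/25 = 22.6% at q = 33% and (4.0 + 2.4)/25 = 25.6% at q = 48%. For b = 16% it is (3.2 + 1.65)/25 = 19.4% and (3.2 + 2.4)/25 = 22.4%.

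**4. False-rejection probability, q = 33% to 48%.**

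| True no-drug rate b | m = 0 | m = 3 | m = 5 | m = 10 |
|---|---|---|---|---|
| 20% | 4.7% | 7.0-10.2% | 8.9-15.9% | 15.3-36.8% |
| 16% | 1.2% | 2.4-3.9% | 3.7-7.6% | 9.0-26.5% |
| 14% | 0.5% | 1.2-2.1% | 2.1-4.8% | 6.6-21.6% |
| 5% | <0.1% | <0.1% | <0.1% | 0.7-5.1% |

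**5. Two boundary checks.**

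- If the residual rate in pre-dosed subjects is itself 20% and b = 20%, the error stays at 4.7%: no inflation.
- If b = 16%, the expected zero-effect rate reaches 20% when the pre-dosed share is (0.20 - 0.16)/(q - 0.16): 23.5% at q = 33%, 12.5% at q = 48%.

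**The case against.** A reader might infer that the one-sided 5% level fails outright, or that a significant Part B result would be a false positive. The documents support neither.

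- **The benchmark has slack.** The 20% was set above every cited rate, and the 3-hour window is longer than the 90-minute endpoint. With a small pre-dosed share and a no-drug rate of 16% or less, the error stays below 5%. This stands. The protocol does not, however, set that slack aside for active drug already on board.
- **The residual rate may be low.** The 33-48% figures follow inhaled dosing at T0. Pre-dosed subjects must have stayed in AF through 45 minutes of monitoring and a recheck just before inhalation (Protocol 6.2.1 B), so they are selected for not having converted. This stands, and it is why q is only an assumption.
- **There may be few such subjects.** Protocol 5.4.1 B bars Class I drugs within a week before enrollment without the exception, and exclusion 28 bars flecainide non-responders. These passages conflict with exclusions 3 and 20. They bear on how many enter, but they do not settle it, and Cohort 4 shows that such subjects were expected.
- **The success rule might already cover earlier flecainide.** The wording on other interventions could be stretched that far, but no timing is stated, and the Cohort 4 efficacy column would then hold no successes.
- **The final SAP already splits the subjects.** It does so only in the three-part pool, without a test, and with missing samples placed among those without flecainide.
- **The Part B SAP versions (4.0 and 4.1) are not available here.** They may have dealt with this, so the point is limited to the protocol and the final SAP.

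**Conclusion.** The mismatch is in the text: a no-drug benchmark, a population that may include subjects pre-dosed for the same episode, and no rule to separate the two effects. Conversions due to the earlier dose can be credited to inhaled flecainide. Inflation of the 5% error is possible, but its size is unknown. It depends on three quantities that the documents leave open: the share pre-dosed, their residual conversion rate and the true no-drug rate. With 5 of 25 pre-dosed, the illustration runs from below 0.1% to 15.9%. The case for action is that attribution is unprotected and a check is cheap, not that the test is shown to be invalid.

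**What to change.** 1. In SAP 9.2.1 and 8.7, report the Part B and Cohort 1 conversion proportions, each with its exact 90% interval, also in mITT subjects who have a measured predose flecainide concentration of 0 and no recorded flecainide for the current episode. Put this beside the all-mITT result as a sensitivity analysis. For Part B, read the subset's interval against 20% when conversion is attributed to inhaled flecainide.
2. Show subjects with a missing predose sample separately, not in Cohort 3. SAP 7.2.5 imputes 0 for a missing T0 value unless other information contradicts it, so the subset must rest on an actual sample. Use the pooled subset so defined whenever the pooled estimate is set against 20%.
3. Report Cohort 4 conversions separately and state that their attribution is uncertain. Do not relabel them all as not due to study drug: any concentration above 0 ng/mL puts a subject in that cohort, which is too weak a ground.
4. Reconcile Protocol 5.4.1 B and exclusion 28 with the flecainide exception in exclusions 3 and 20.

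**Cost.** Some SAP wording and a few table columns; predose PK and prior medication are already collected. The subset is smaller: if 20 of 25 remain, the exact test rejects at 8 or more, with size 3.2% and power 83% at 48%, against 92% for 25. SAP 9.3 shows that the Part B analysis is complete, so the repeat is post hoc and cannot restore error control for that test.
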